10.1 MAIN ANALYSIS

Analysis of the primary outcome

- Change of each of the Kansas City Cardiomyopathy Questionnaire (KCCQ) scores [clinical summary score (CSS), total symptom score (TSS), overall summary score (OSS)] from index date 1 to index date 2 (= 24 weeks after index date 1) in patients newly treated with empagliflozin according to routine practice

will be performed according to the analysis manual for the KCCQ. Changes in the KCCQ scores will be calculated for each patient. Results will be presented as N, mean, standard deviation, median, minimum and maximum values as well as number of missings as extra column. A change of 5 points of OSS will be considered as clinically meaningful.

In addition, change from index date 1 in clinical summary score for HF symptoms and physical limitations domains of the KCCQ at week 24 will be evaluated by subgroups based on age at index date 1 (<50/50-<65/65-<75/≥75 years as well as <65/≥65 years), gender, country, baseline LVEF (HFrEF, HFmrEF HFpEF), and status of diabetes mellitus at visit 1. All recorded data for efficacy up to week 24 will be included.

For analysis of the secondary outcome

- Change of the New York Heart Association (NYHA) Class from index date 1 to index date 2 (= 24 weeks after index date 1) in patients newly treated with empagliflozin tabulation of relative and absolute frequencies will be presented as well as a shift table.

For the analysis of the secondary outcome

- Capture of real-world patterns of patient characteristics, clinical disease presentation and therapeutic regimen chosen in participants with chronic HF as well as of patient reported outcome at visit 1

tabulations of relative and absolute frequencies will be presented. Comparison of data at visit 1 between patients receiving empagliflozin or not for treatment of HF will be performed by Chi- quadrat-test or Mann-Whitney-U-test or Student t-Test.

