9.3 VARIABLES

The following parameters will be collected at **visit 1** (= index date 1) of all registered patients:

1. Patient demographics:
 - Year of birth
 - Gender
 - Height, weight, BMI (will be calculated from height and weight)
2. Date of first diagnosis of HF
3. Etiology of heart failure
 - Coronary artery disease
 - Hypertension
 - Valve disease
 - Cardiomyopathy
 - Congenital heart disease
 - Drug induced
 - Infective
 - Storage disorders
 - Diabetes
 - Obesity
 - Other
4. Clinical parameters relevant for HF (last available value and date when it was collected) as valid at baseline and performed during clinical routine:
 - LVEF
 - Current NYHA Class according to treating physician
 - Electrocardiogram (ECG)
 - Heart rate
 - Blood pressure (systolic, diastolic)
 - Laboratory diagnostic according to clinical routine (last available value and date when it was collected):
 - BNP (B-type natriuretic peptide) and/or pro-BNP (N-terminal pro-B-type natriuretic peptide)
 - Lipids (cholesterol, HDL, LDL)
 - Blood urea nitrogen (BUN)
 - Serum creatinine

- Sodium, potassium
- Complete blood count
- 6-min-walking test according to clinical routine

5. Alcohol consumption and smoking status (non-smoker, previous smoker, current smoker)
6. Concomitant diseases / Comorbidities
 - Disease according to ICD-10 (diabetes, hypertension, coronary artery disease, infarction, chronic kidney disease, atrial fibrillation, cancer, other)
 - Date of first diagnosis
7. Previous HF hospitalizations within the last 6 months
8. HF related medication used in the last 6 months
 - Medication
 - Indication
 - Application
 - Dose
 - Start date, end date, continuing
9. Current HF related and other relevant concomitant medication
 - Medication
 - Indication
 - Application
 - Dose
 - Start date, end date, continuing
10. Newly prescribed treatment regime:
 - Date of prescription
 - Medication (empagliflozin and / or other drug)
 - Reason, if no prescription of empagliflozin
11. Patient reported outcomes:
 - KCCQ (23 items) completed by patients during the visit

The following parameters will be collected at routine **visit 2** [= index date 2: 24 weeks (± 2 weeks) after index date 1] only of registered patients treated with empagliflozin:

1. Weight, BMI (will be calculated from height and weight)
2. Clinical parameters relevant for HF performed during clinical routine (last available value and date when it was collected):
 - LVEF

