**9.3.3 Covariates**

Covariates for adjustment will include patient demographics and disease characteristics. These will be discussed in the Statistical Analysis Plan (SAP).

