9.5 STUDY SIZE

With no formal a-priori hypotheses, this observational study uses a hypothesis-free approach focused on descriptive analyses. Thus, no formal sample size calculation is provided. The study is designed to describe the use of empagliflozin and PRO in clinical routine. In the 8 participating countries sites in urban as well as rural areas will be included. The nationwide distribution of the participating sites and the number of 4600 patients enrolled are intended to ensure that the data

collected are representative. Based on random identification, it is expected that about 3300 patients will receive empagliflozin. The large sample size overall was chosen to support a large range of analyses from general scientific questions to specific regional or subgroup questions with sufficient precision. A minimum target number of 100 patients per country is chosen to provide reasonable sample size for scientific questions applicable across countries and subgroups of interest. The sample size will ensure that the descriptive data are sufficiently precise and meaningful at a country or subgroup level.

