9.7.1 Main analysis

Analysis of the primary outcome

- Change of each of the Kansas City Cardiomyopathy Questionnaire (KCCQ) scores [clinical summary score (CSS), total symptom score (TSS), overall summary score (OSS)] from index date 1 to index date 2 (= 24 weeks after index date 1) in patients newly treated with empagliflozin according to routine practice

will be performed according to the analysis manual for the KCCQ. Changes in the KCCQ scores will be calculated for each patient. Results will be presented as N, mean, standard deviation, median, minimum and maximum values as well as number of missings as extra column. A change of 5 points of OSS will be considered as clinically meaningful.

Change from index date 1 in clinical summary score for HF symptoms and physical limitations domains of the KCCQ at week 24 will be evaluated further by subgroup analyses based on age at index date 1, gender, country, baseline LVEF (rEF, mpEF pEF), and status of diabetes mellitus at visit 1. All recorded data for efficacy up to week 24 will be included.

[figure not shown]
Analysis of the secondary outcome

- Change of the New York Heart Association (NYHA) Class from index date 1 to index date 2 (= 24 weeks after index date 1) in patients newly treated with empagliflozin
tabulation of relative and absolute frequencies will be presented.

For the analysis of the secondary outcome

- Capture of real-world patterns of patient characteristics, clinical disease presentation and therapeutic regimen chosen in participants with chronic HF as well as of patient reported outcome at visit 1

tabulations of relative and absolute frequencies will be presented. Comparison of data at visit 1 between patients receiving empagliflozin or not for treatment of HF will be performed by Chi-quadrat-test or Mann-Whitney-U-test.

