9.9 LIMITATIONS OF THE RESEARCH METHODS

This is a single arm non-interventional study based on newly collected data with the aim to gather data of HF treatment as well as PRO in clinical routine. Generally, a NIS is the most suitable instrument for obtaining information about the use of medicines in everyday clinical practice. The eligibility criteria are non-restrictive which will permit the enrolment of a broad patient population. Thus, patients are more different in baseline characteristics and disease data than patients enrolled into a clinical trial. The choice of treatment and performance of examinations is at the discretion of the investigator. Therefore, results of disease specific examinations recorded may comprise various time periods. There may also be more missing values as in clinical trials, since the non-interventional nature means that no specification is provided on examinations to be carried out.

Selection bias could occur at the site level and the patient level. The site of the patient selection may affect the outcomes given patient differences across practice sites. To minimize the site level selection

bias, the goal is to have a great number of participating centers. To minimize selection bias at the patient level, consecutive enrolment is performed. Additionally, a non-empagliflozin treated cohort is added in order to get an overview of the HF patients at the respective sites.

Information bias will be minimized by the use of standard eCRF and validated patient questionnaire as well as by physicians' training on the study protocol.

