7.3 COVARIATES

Demographics and disease characteristics will be used to define subgroups of interest.

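### Does the unadjusted visit 1 comparison of the two cohorts need adjustment or stratification by country?

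*SAP*

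**What the plan says.** Protocol section 9.3.3 reads: "Covariates for adjustment will include patient demographics and disease characteristics. These will be discussed in the Statistical Analysis Plan (SAP"). SAP section 7.3 takes up the topic in one sentence: "Demographics and disease characteristics will be used to define subgroups of interest".

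The analysis sections do not mention adjustment. Protocol section 9.7.1 states: "Comparison of data at visit 1 between patients receiving empagliflozin or not for treatment of HF will be performed by Chi-quadrat-test or Mann-Whitney-U-test". SAP section 10.1 opens with the same words, "Comparison of data at visit 1 between patients receiving empagliflozin or not for treatment of HF will be performed by", names the same two tests and adds the Student t-test. Visit 1 data are analysed in the full analysis set, which holds both cohorts (SAP section 10). Country appears in SAP section 10.1 only as a subgroup for the 24-week change in the clinical summary score, which covers empagliflozin patients alone.

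Protocol section 9.7 calls all methods descriptive and exploratory, confidence intervals and p-values included. Protocol section 9.5 states that there are no a-priori hypotheses. The secondary objective (Protocol section 8, SAP section 5.2) is to record patient characteristics and disease presentation by the regimen chosen.

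**The concern.** Two things look wrong. First, the protocol promises covariates for adjustment and the SAP turns them into subgroup variables without giving a reason. Protocol section 9.7.1 already had only crude tests, so part of the conflict lies inside the protocol.

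Second, treatment is the physician's choice, and there is no quota by cohort within country. Protocol section 9.5 justifies the study size at country level: "The sample size will ensure that the descriptive data are sufficiently precise and meaningful at a country or subgroup level". Protocol section 9.9 concedes that "The site of the patient selection may affect the outcomes given patient differences across practice sites". If countries with high empagliflozin uptake also enrol patients with better or worse health status, a crude difference between cohorts partly reflects country. With about 3300 against 1300 patients, even a small shift can reach p < 0.05, and a reader might take it for a feature of prescribing within each country.

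A side issue is that Protocol section 9.3 records the new regimen as "Medication (empagliflozin and / or other drug"), yet the KCCQ change is not tabulated by whether another heart failure drug was started on the same day.

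**Working it through.** The plan states no figure for this comparison, so there is none to reproduce. The check has two parts: how large the country effect could be, and whether the texts call for removing it.

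**Inputs from the documents.** About 4600 patients and about 3300 expected on empagliflozin (Protocol section 9.5), hence 4600 − 3300 = 1300 in the other cohort. There are 8 countries with a minimum of 100 patients each. The protocol abstract gives about 7000 patients; the 4600 of the protocol body and the SAP is used here.

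**Assumed inputs.** KCCQ SD 22, no regimen difference within any country, equal country sizes, and the country spreads listed below. None of these is in the documents.

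**Formula.** Let p be a country's empagliflozin share and m its KCCQ mean. With equal country sizes, the crude cohort difference is Cov(p, m) / [p̄(1 − p̄)] = r × SD(p) × SD(m) / [p̄(1 − p̄)], where r is the correlation between p and m across countries.

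- p̄ = 3300/4600 = 0.717, so p̄(1 − p̄) = 0.2027.
- SE of the crude difference = 22 × √(1/3300 + 1/1300) = 0.720, so p < 0.05 needs about 1.96 × 0.720 = 1.41 points.

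| Assumed spread across countries | r | Crude difference | z |
|---|---|---|---|
| Shares 56–87% (SD 0.10), means 54–66 (SD 4) | 1 | 0.10 × 4 / 0.2027 = 1.97 | 2.74 |
| Same | 0.5 | 0.99 | 1.37 |
| Same | 0 | 0 | 0 |
| Shares 64–79% (SD 0.05), means 57–63 (SD 2) | 1 | 0.05 × 2 / 0.2027 = 0.49 | 0.68 |
| Two countries, 90% vs 53.5%, 10 points apart | 1 | 0.1825 × 5 / 0.2027 = 4.50 | 6.25 |

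A simulation of 8 × 575 patients (2000 runs) agrees. The crude test rejects in 76% of runs in the first row, 6% in the third and 11% in the fourth. With country in the model it rejects in 6% for the first row and 4% for the fourth.

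The arithmetic shows that an effect is possible but not that it is likely, since the answer is set by the assumed spreads and r.

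**What the texts ask for.**

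1. Section 9.3.3 names demographics and disease characteristics. It does not name country, and it does not say which analysis would be adjusted.
2. Those characteristics are largely the outcomes of the visit 1 table. Adjusting that table for them would amount to adjusting it for itself, so section 9.3.3 cannot sensibly refer to it. Stratifying by country would not fulfil section 9.3.3 either.
3. The objective is a description by regimen chosen. If uptake differs by country, that is part of who received which regimen among the enrolled patients. A country-stratified difference answers a different question.
4. SAP section 3 bases the SAP on Protocol section 9.7, and section 9.7.1 plans unadjusted tests. The SAP follows the section that sets out the analysis.
5. The site sentence in Protocol section 9.9 concerns selection bias among about 1000 sites. Strata for 8 countries would not remove differences among sites.

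**The case for a change.** The strongest case for a change is that the mismatch between Protocol section 9.3.3 and SAP section 7.3 is certain and needs no assumption. The visit 1 contrast is a named secondary outcome that will be formally tested. Country is already recorded, and the stratified estimate costs little precision: with shares of 90% and 53.5%, its SE is 22 / √(2300 × 0.90 × 0.10 + 2300 × 0.535 × 0.465) = 0.788, against 0.720 crude, about 9% wider. Separate country tables would be a weak substitute, since at 100 patients (about 72 vs 28) the 95% half-width is 1.96 × 22 × √(1/72 + 1/28) = 9.6 points.

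The textual mismatch stands, as does the arithmetic. The step from there to a required analysis does not. The 9.6 points apply only at the country minimum; at 575 per country (about 412 vs 163) the same formula gives about 4.0. Stratified tests for every visit 1 item would cover 11 etiologies, 8 comorbidity categories, laboratory values and medications, and would double a set of exploratory p-values without changing what the table describes.

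Nor can it be said that adjustment is absent everywhere. The public numbering jumps from 9.7.1 to 9.7.3 in the protocol and from 10.1 to 10.3 in the SAP, and the table shells are a separate document. What those places hold is unknown, so their absence cannot be counted against the plan.

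The table of KCCQ change by co-started drug concerns neither the cohort comparison nor country. It is an optional display.

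**Conclusion.** No change to the plan follows. The crude visit 1 comparison is a sound description of the enrolled patients by regimen, which is what the secondary objective asks for, and it affects neither the primary KCCQ change nor any confirmatory claim. The shift that country mix could add to a visit 1 KCCQ difference lies between 0 and 4.5 points under assumed spreads and SD 22. It is nil if uptake and patient mix do not vary together, and the documents give no country-level data to narrow that range. A country-stratified display would be a reasonable supportive extra, but statisticians could fairly differ on whether it adds anything.

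The difference between the two covariate sentences is a slip in wording. An analyst working from Protocol section 9.7.1 and SAP section 10.1 would run the same tests either way. The conclusion rests on the comparison being reported as descriptive, with exploratory p-values, as Protocol section 9.7 states.

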Variables:	Patient demographics (Year of birth, gender, height, weight) Date of first diagnosis of HF , etiology of HF Clinical parameters relevant for HF [LVEF, current NYHA Class according to treating physician, electrocardiogram (ECG), heart rate, blood pressure (systolic, diastolic), laboratory diagnostic according to clinical routine (last available value and date when it was collected), 6-min-walking test according to clinical routine] Alcohol consumption and smoking status (non-smoker, previous smoker, current smoker) Concomitant diseases / Comorbidities Previous HF hospitalizations within the last 6 months HF related medication used in the last 6 months Current HF related and other relevant concomitant medication Newly prescribed treatment regime [Date of prescription, medication (empagliflozin and / or other drug), reason, if no prescription of empagliflozin] Patient reported outcomes (KCCQ 23 items) Date of discontinuation of empagliflozin treatment, reason (if applicable)		

Name of company: Boehringer Ingelheim			
Name of finished medicinal product: Jardiance®			
Name of active ingredient: empagliflozin			
Protocol date: 24.Jan.2022	Study number: 1245-0259	Version/Revision: 3.0	Version/Revision date: 30 September 2022
Variables for safety evaluation: ADRs (serious and non-serious), fatal adverse events (AEs), pregnancies, HF related hospitalizations			
Data sources:	
Medical records collected through routine clinical care will be used for patient demographic, disease relevant data and medication data.
 
Patient reported outcome:
 
All enrolled patients have to complete the KCCQ at index date 1, whereas only patients treated with empagliflozin were asked to fill in the KCCQ at index date 2.
		
Study size:	
It is planned that data of approximately 7000 HF patients in 8 countries will be collected (Poland, Romania, Hungary, Switzerland, Czech Republic, Bulgaria, Slovenia, Serbia).
		

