9.2.1 Study sites

It is planned to collect data of approximately 4600 patients by approximately 1000 sites in 8 countries located in central east Europe (CEE): Switzerland, Poland, Romania, Hungary, Czech Republic, Bulgaria, Slovenia and Serbia). It is strived to include a minimum of about 3300 patients starting with empagliflozin treatment.

It is expected that each participating site will enroll 5 patients to ensure country-specific representativeness of collected data, so that a minimum target number of 100 patients per country will be reached.

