6.2 SETTING

In this NISnd, data from a total of about 4600 HF patients will be collected during routine clinical practice by private practice and clinics in 8 countries (Poland, Romania, Hungary, Switzerland, Czech Republic, Bulgaria, Slovenia, and Serbia).

There will be no procedure outside routine clinical practice except for handing out the KCCQs to the enrolled patients by the study staff. The physician's decision to initiate treatment with empagliflozin or a non-SGLT2i HF drug is independent of the registration of the patient in this study. A patients with documented baseline evaluation is considered enrolled.

This study is planned to observe patients treated with empagliflozin for approximately 24 weeks, whereas data of the comparison group are collected at visit 1 exclusively. In addition to data collected by the physician, all patients should fill in the KCCQ-questionnaire at visit 1, whereas only patients receiving empagliflozin must fill in the questionnaire after approximately 24 weeks to address the change in disease specific symptoms and items

regarding physical functioning and self-care during empagliflozin therapy in a real-world patient population.

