9.3 HANDLING OF INCONSISTENCIES IN DATA AND OUTLIERS

Not planned.

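### The Student t-test that SAP 10.1 adds for the visit 1 cohort comparison should be the unequal-variance (Welch) version, because the two cohorts are planned at about 3300 and 1300 (minor)

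*SAP*

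**What the plan says.** Protocol 9.7.1 says that the comparison of visit 1 data between patients who do and do not receive empagliflozin "will be performed by Chi-quadrat-test or Mann-Whitney-U-test". SAP 10.1 covers the same comparison and extends the list, which now ends "Mann-Whitney-U-test or Student t-Test". The t-test is therefore new in the SAP. Neither document mentions an unequal-variance version or a check of variances, and neither says which continuous variables get which test.

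On cohort sizes, Protocol 9.5 refers to "the number of 4600 patients enrolled" and adds that "it is expected that about 3300 patients will receive empagliflozin". SAP 6.2 agrees on the total: "data from a total of about 4600 HF patients will be collected". Protocol 9.2.1 treats the empagliflozin figure as a floor: "It is strived to include a minimum of about 3300 patients starting with empagliflozin treatment". The protocol abstract gives a different total: "It is planned that data of approximately 7000 HF patients in 8 countries will be collected".

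Protocol 9.7 describes the study's p-values as exploratory. No significance level is stated for this comparison.

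**The concern.** The pooled t-test estimates one common variance and uses it for both groups. With equal group sizes this does little harm when the true variances differ. With unequal sizes the pooled estimate is dominated by the larger group, so the standard error of the difference is wrong. It is too small when the smaller group is the more variable one, and too large when it is the less variable one. The size of the error depends on the ratio of the group sizes and the ratio of the SDs. It does not shrink as the total grows.

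The cohorts here are formed by the physician's treatment decision, so nothing in the design makes their spread equal. At stake are the p-values for whichever continuous visit 1 variables are given the t-test (age, BMI, blood pressure, LVEF, laboratory values and KCCQ scores are all collected). They could overstate or understate the evidence that the cohorts differ.

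**Working it through.** The plan has no power or error calculation for this comparison, so there is no figure of its own to reproduce.

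**Inputs**
- Larger cohort: n1 = 3300 (Protocol 9.5).
- Smaller cohort: n2 = 4600 − 3300 = 1300. This is a subtraction, not a stated figure. The split is 3300/1300 = 2.54 to 1.
- Nominal two-sided level 5%: assumed.
- r = SD of the smaller cohort divided by SD of the larger: assumed, over a range.

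**Formula.** Set the larger cohort's SD to 1. The ratio k of the pooled to the true standard error satisfies, apart from negligible degrees-of-freedom terms,

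k² = (n1 + n2·r²) / (n2 + n1·r²).

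The true level is 2·[1 − Φ(1.96·k)].

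**Results for 3300 and 1300**

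| r | k² | k | true level |
|---|---|---|---|
| 0.8 | 4132/3412 = 1.211 | 1.100 | 3.1% |
| 0.9 | 4353/3973 = 1.096 | 1.047 | 4.0% |
| 1.0 | 1 | 1 | 5.0% |
| 1.1 | 4873/5293 = 0.921 | 0.960 | 6.0% |
| 1.2 | 5172/6052 = 0.855 | 0.924 | 7.0% |
| 1.5 | 6225/8725 = 0.713 | 0.845 | 9.8% |

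**Check by simulation** (normal data, 20,000 runs per setting). With the larger cohort's SD at 0.8 times the smaller's (r = 1.25), the pooled test rejected in 7.6% of runs, against 7.5% by formula. With it at 1.25 times (r = 0.8), it rejected in 2.9%, against 3.1%. The Welch test stayed between 4.7% and 5.2% for SD ratios from 0.5 to 2.

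**Sensitivity to the abstract's total of 7000**
- Same 2.54 to 1 split (about 5022 and 1978): the levels do not change, because k depends only on the two ratios.
- 3300 held fixed, so 7000 − 3300 = 3700 in the other cohort: the groups are nearly equal, and the level stays between 4.3% and 5.8% even for SD ratios from 0.5 to 2.

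**Cost of Welch when the SDs are equal.** The Satterthwaite degrees of freedom are (1/3300 + 1/1300)² / [(1/3300)²/3299 + (1/1300)²/1299] ≈ 2380, against 4598 for the pooled test. The 5% critical values are about 1.961 and 1.960, so there is practically no loss of power.

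**The case against.** The strongest reply is that little hangs on these p-values. The study is declared free of prior hypotheses, the p-values are exploratory, and no level is set that could be violated. The comparison is a secondary visit 1 description, and SAP section 10 reports means, SDs and percentiles in any case. In absolute terms the effect is small. With r = 1.2, the smallest mean difference reaching p < 0.05 is 1.96·√0.0012055 = 0.068 of the larger cohort's SD under the pooled test, and 1.96·√0.0014107 = 0.074 under Welch, a shift of about 0.006 SD. Cohorts chosen by physicians are also unlikely to have exactly equal means, so the error rate under an exact null is a limited measure of harm. All of this stands, and it makes the point minor. It does not justify a pooled test when one that holds its level costs nothing.

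Three stronger readings go beyond the documents:
- *The p-values are wrong.* A reader might infer this, but no SD is given for either cohort, and both share the same disease and largely the same eligibility criteria. Unequal spread is possible, not shown. That Student's test means the pooled version is ordinary usage, although the SAP does not say so.
- *The open list lets the analyst run both tests and keep the smaller p-value.* Nothing in the SAP says this. The list also contains the chi-square test and reads naturally as a menu by variable type. The table shells, a separate document not available here, may assign the tests.
- *Mann-Whitney is the safe alternative.* It is also disturbed by unequal spread. With equal means it rejected in about 9.6% of 2,000 simulated runs when the larger cohort's SD was half the smaller's, and in about 3% when it was double.

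**Conclusion.** The point holds as a minor improvement in method. SAP 10.1 names a test whose usual form assumes equal variances, for two physician-selected cohorts planned at about 3300 and 1300. If the SDs differ by 20% to 50%, a nominal 5% test runs at about 3% to 10%, depending on which cohort is more variable. If they differ by no more than about 10%, it runs at about 4% to 6%.

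This rests on the assumed 5% level, the assumed SD ratios, and a 1300 obtained by subtraction from the total in the protocol body and the SAP. If the abstract's 7000 applied with 3300 held fixed, the effect would nearly vanish. The primary outcome, a within-cohort description of KCCQ change, is unaffected.

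**What to change.** In SAP 10.1, replace Student's t-test with the unequal-variance (Welch/Satterthwaite) t-test for comparisons of means. In the same sentence, state which continuous variables are compared by Welch and which by Mann-Whitney, and note that Mann-Whitney tests for a shift in distribution and not for equality of means.

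The cost is one sentence. The standard SAS t-test procedure already prints the Satterthwaite result, so no new programming is needed, and nothing changes in data collection or sample size.
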